### Assessment of Causality as per Investigator

The investigator is obligated to assess the relationship between study treatment and each occurrence of each AE/SAE.

A *reasonable possibility* of a relationship conveys that there are facts, evidence, and/or arguments to suggest a causal relationship, rather than a relationship cannot be ruled out.

The investigator will use clinical judgment to determine the relationship.

Alternative causes, such as underlying disease(s), concomitant therapy, and other risk factors, as well as the temporal relationship of the event to study treatment administration will be considered and investigated.

The investigator will also consult the investigator's brochure (IB) and/or product information, for marketed products, in his/her assessment.

For each AE/SAE, the investigator **must** document in the medical notes that he/she has reviewed the AE/SAE and has provided an assessment of causality.

There may be situations in which an SAE has occurred and the investigator has minimal information to include in the initial report to the sponsor. However, **it is very important that the investigator always make an assessment of causality for every event before the initial transmission of the SAE data to the sponsor.**

The investigator may change his/her opinion of causality in light of follow-up information and send an SAE follow-up report with the updated causality assessment.

The causality assessment is one of the criteria used when determining regulatory reporting requirements.

### SAE Reporting to the sponsor via Paper CRF

Facsimile transmission of the SAE Reporting Form is the preferred method to transmit SAE information to the sponsor.

In rare circumstances and in the absence of facsimile equipment, notification by telephone is acceptable with a copy of the SAE data collection tool sent by overnight mail or courier service.

Initial notification via telephone does not replace the need for the investigator to complete and sign the SAE Reporting Form within the designated reporting time frames.

Contacts for SAE reporting can be found in the protocol title page.

AGN-242428

## 12.4. Appendix 4: Contraceptive Guidance and Collection of Pregnancy Information

### Definitions

#### **Woman of Childbearing Potential (WOCBP)**

A woman is considered fertile following menarche and until becoming postmenopausal unless permanently sterile (see below).

#### **Women in the following categories are not considered WOCBP:**

1. Premenarchal
2. Premenopausal female with 1 of the following:
  - Documented hysterectomy
  - Documented bilateral salpingectomy
  - Documented bilateral oophorectomy
3. Postmenopausal female
  - A postmenopausal state is defined as no menses for 12 months without an alternative medical cause.
  - Females on HRT and whose menopausal status is in doubt will be required to use one of the non-estrogen hormonal highly effective contraception methods if they wish to continue their HRT during the study. Otherwise, they must discontinue HRT to allow confirmation of postmenopausal status before study enrollment.

### Contraception Guidance

#### Male Participants

Male participants with female partners of childbearing potential are eligible to participate if they agree to ONE of the following during the study and for 30 days following the last dose of study treatment:

- Are abstinent from penile-vaginal intercourse as their usual and preferred lifestyle (abstinent on a long-term and persistent basis) and agree to remain abstinent
- Agree to use a male condom plus partner use of a contraceptive method with a failure rate of < 1% per year when having penile-vaginal intercourse with a WOCBP who is not currently pregnant

AGN-242428

Men with a pregnant or breastfeeding partner must agree to remain abstinent from penile-vaginal intercourse or use a male condom during each episode of penile penetration during the study and for 30 days following the last dose of study treatment.

In addition, male participants must refrain from donating sperm for the duration of the study and for 30 days following the last dose of study treatment.

The same highly effective method of contraception must be used consistently and correctly throughout the study.

## Female Participants

Female participants of childbearing potential are eligible to participate if they agree to use 2 forms of birth control, in which at least 1 form must be a highly effective method of contraception, consistently and correctly as tabulated below. Of note, both forms can be highly effective if preferred, but at least 1 form must be highly effective.

Highly Effective Contraceptive Methods That Are User Dependenta	
Failure rate of < 1% per year when used consistently and correctly.	
Combined (estrogen- and progestogen-containing) hormonal contraception associated with inhibition of ovulation 
 
• Oral
 
• Intravaginal
 
• Transdermal
 
	
Progestogen-only hormonal contraception associated with inhibition of ovulation 
 
• Oral
 
• Injectable
 
	
Highly Effective Methods That Are User Independenta	
Implantable progestogen-only hormonal contraception associated with inhibition of ovulation 
 
• Intrauterine device (IUD)
 
• Intrauterine hormone-releasing system (IUS)
 
• Etonogestrel implant (ie, Nexplanon®)
 
	
Bilateral tubal occlusion	
Intrauterine copper contraceptive (ie, ParaGard ® )	
Vasectomized Partner	
A vasectomized partner is a highly effective contraception method provided that the partner is the sole male sexual partner of the women of childbearing potential (WOCBP) and the absence of sperm has been confirmed. If not, an additional highly effective method of contraception should be used.	
Sexual Abstinence	
Sexual abstinence is considered a highly effective method only if defined as refraining from heterosexual intercourse during the entire period of risk associated with the study treatment. The reliability of sexual abstinence needs to be evaluated in relation to the duration of the study and the preferred and usual lifestyle of the participant.	

The list in this table is not all inclusive.

a Typical use failure rates may differ from those when used consistently and correctly. Use should be consistent with local regulations regarding the use of contraceptive methods for participants participating in clinical studies.

Acceptable birth control methods that result in a failure of more than 1% per year (and are thus, not classified as highly effective) include the following noted below. One of these methods can be used as the required second method of contraception, if desired:

AGN-242428

- Progestogen-only oral hormonal contraception, where inhibition of ovulation is not the primary mode of action
- Male or female condom with or without spermicide
- Cap, diaphragm, or sponge with spermicide

A combination of male condom with either cap, diaphragm, or sponge with spermicide (double barrier methods) are also considered acceptable, but not highly effective, birth control methods.

### **Pregnancy Testing**

WOCBP should only be included after a confirmed menstrual period and a negative highly sensitive urine pregnancy test.

Additional pregnancy testing should be performed as outlined in schedule of activities during the treatment period and at the follow-up visit or upon early termination. Pregnancy testing will be performed whenever a menstrual cycle is missed or when pregnancy is otherwise suspected at the investigator's discretion.

Pregnancy testing, with a sensitivity of at least 25 mIU/mL will be performed at the study site with testing materials provided by the central laboratory.

### **Collection of Pregnancy Information**

#### **Male Participants with Partners Who Become Pregnant**

The investigator will attempt to collect pregnancy information on any male participant's female partner who becomes pregnant while the male participant is in this study. This applies only to male participants who receive study medication.

After obtaining the necessary site specific signed informed consent from the pregnant female partner directly, the investigator will record pregnancy information on the appropriate form and submit it to the sponsor within 24 hours of learning of the partner's pregnancy. The female partner will also be followed to determine the outcome of the pregnancy. Information on the status of the mother and child will be forwarded to the sponsor. Generally, the follow-up will be no longer than 6 to 8 weeks following the estimated delivery date. Any termination of the pregnancy will be reported regardless of fetal status (presence or absence of anomalies) or indication for the procedure.

#### **Female Participants Who Become Pregnant**

The investigator will collect pregnancy information on any female participant who becomes pregnant while participating in this study. Information will be recorded on the appropriate form and submitted to the sponsor within 24 hours of learning of a participant's pregnancy.

The participant will be followed to determine the outcome of the pregnancy. The investigator will collect follow-up information on the participant and the neonate, and the information will be

AGN-242428

forwarded to the sponsor. Generally, follow-up will not be required for longer than 6 to 8 weeks beyond the estimated delivery date. Any termination of pregnancy will be reported, regardless of fetal status (presence or absence of anomalies) or indication for the procedure.

While pregnancy itself is not considered to be an AE or SAE, any pregnancy complication will be reported as an AE or SAE. A spontaneous abortion and an elective termination of a pregnancy are always considered to be SAEs and will be reported as such. Any poststudy pregnancy-related SAE considered reasonably related to the study treatment by the investigator will be reported to the sponsor as described in Section 9.2. While the investigator is not obligated to actively seek this information in former study participants, he or she may learn of an SAE through spontaneous reporting.

Any female participant who becomes pregnant while participating in the study will discontinue study treatment immediately and be withdrawn from the study.

AGN-242428

## 12.5. Appendix 5: Standard Discontinuation Criteria

CDISC Submission Value	CDISC Definition
Adverse event	Any untoward medical occurrence in a patient or clinical investigation participant administered a pharmaceutical product and which does not necessarily have a causal relationship with this treatment. An adverse event (AE) can therefore be any unintended sign (including an abnormal laboratory finding), symptom, or disease temporally associated with the use of a medicinal (investigational) product, whether or not related to the medicinal (investigational) product. For further information, see the ICH Guideline for Clinical Safety Data Management: Definitions and Standards for Expedited Reporting. [Modified from ICH E2A] Synonyms: side effect, adverse experience. See also serious adverse event, serious adverse experience. (CDISC glossary)
Completed	To possess every necessary or normal part or component or step; having come or been brought to a conclusion (National Cancer Institute [NCI])
Death	The absence of life or state of being dead (NCI)
Disease relapse	The return of a disease after a period of remission
Failure to meet randomization criteria	An indication that the participant has been unable to fulfill/satisfy the criteria required for assignment into a randomized group
Lack of efficacy	The lack of expected or desired effect related to a therapy (NCI)
Lost to follow-up	The loss or lack of continuation of a participant to follow-up
Non-compliance with study treatment	An indication that a participant has not agreed with or followed the instructions related to the study medication (NCI)
Other	Different than the one(s) previously specified or mentioned (NCI)
Physician decision	A position, opinion or judgment reached after consideration by a physician with reference to participant (NCI)
Pregnancy	Pregnancy is the state or condition of having a developing embryo or fetus in the body (uterus), after union of an ovum and spermatozoon, during the period from conception to birth (NCI)
Progressive disease	A disease process that is increasing in extent or severity (NCI)

AGN-242428

CDISC Submission Value	CDISC Definition
Protocol deviation	An event or decision that stands in contrast to the guidelines set out by the protocol (NCI)
Recovery	A healing process and/or an outcome implying relative health. The term is typically used in the context of direct and indirect effects of sickness or injury (NCI)
Screen failure	The potential participant who does not meet one or more criteria required for participation in a trial
Site terminated by sponsor	An indication that a clinical study was stopped at a particular site by its sponsor (NCI)
Study terminated by sponsor	An indication that a clinical study was stopped by its sponsor (NCI)
Technical problems	A problem with some technical aspect of a clinical study, usually related to an instrument (NCI)
Withdrawal by parent/guardian	An indication that a study participant has been removed from the study by the parent or legal guardian
Withdrawal by participant	An indication that a study participant has removed itself from the study (NCI)

AGN-242428

## 12.6. Appendix 6: Liver Safety: Suggested Actions and Follow-up Assessment

**Phase II** liver chemistry stopping criteria are designed to assure participant safety and to evaluate liver event etiology.

### Phase II Liver Chemistry Stopping Criteria and Follow-Up Assessments

Liver Chemistry Stopping Criteria	
AST and/or ALT-absolute	AST and/or ALT $\geq 5 \times$ ULN
AST and/or ALT Increase	AST and/or ALT $\geq 3 \times$ ULN persists for $\geq 4$ weeks
Bilirubin or INR	AST and/or ALT $\geq 3 \times$ ULN and TBL $\geq 2 \times$ ULN or INR $> 1.5$
Cannot Monitor	AST and/or ALT $\geq 3 \times$ ULN and cannot be monitored weekly for 4 weeks
Symptomatica	AST and/or ALT $\geq 3 \times$ ULN associated with symptoms (new or worsening) believed to be related to liver injury or hypersensitivity
Potential Hy's Law cases	
AST, ALT, and Bilirubinb	AST and/or ALT $\geq 3 \times$ ULN and TBL $\geq 2 \times$ ULN and alkaline phosphatase $< 2 \times$ ULN

AGN-242428

Required Actions and Follow-up Assessments	
Actions	Follow-Up Assessments

 
• Immediately discontinue study treatment.
 
• Report the event to the sponsor within 24 hours.
 
• Complete the liver event eCRF, and complete a serious adverse event (SAE) data collection tool if the event also met the criteria for an SAE.b
 
• Perform liver chemistry follow-up assessments.
 
• Monitor the participant until liver chemistry test abnormalities resolve, stabilize, or return to baseline (see MONITORING).
 
• Do not restart/rechallenge participant with study treatment
 
• As restart/rechallenge is not allowed per protocol, permanently discontinue study treatment and continue participant in the study for any protocol specified follow-up assessments
 
	
 
• Viral hepatitis serology and other laboratory testing, as well as anti-nuclear antibody and anti-smooth muscle antibodyc
 
• Obtain INR and recheck with each liver chemistry assessment until the transaminases values show downward trend
 
• Obtain blood sample for pharmacokinetic (PK) analysis 48 hours after the most recent dosed
 
• Serum creatine phosphokinase (CPK) and lactate dehydrogenase (LDH)
 
• Fractionate bilirubin, if TBL <math>\geq 2 \times</math> ULN
 
• Obtain complete blood count with differential to assess eosinophilia
 
• Record the appearance or worsening of clinical symptoms of liver injury, or hypersensitivity, on the adverse event (AE) report form
 
• Record use of concomitant medications (including acetaminophen, herbal remedies, and other over-the-counter medications) on the concomitant medications eCRF.
 
• Record alcohol use on the liver event alcohol intake eCRF
 
 
If AST and/or ALT <math>\geq 3 \times</math> ULN AND bilirubin <math>\geq 2 \times</math> ULN:
 
 
• Repeat liver chemistry tests (include alanine transferase (ALT), aspartate transaminase [AST], alkaline phosphatase [ALP], total, direct, and indirect, bilirubin [TBL, DBL, IBL], gamma-glutamyl transferase [GGT], and lactate dehydrogenase [LDH]) and perform liver event follow-up assessments within 24 hours.
 
• Monitor participant twice weekly until liver chemistry test abnormalities resolve, stabilize, or return to baseline.
 
• A specialist or hepatology consultation is recommended.
 
 
If AST and/or ALT <math>\geq 3 \times</math> ULN AND bilirubin <math>< 2 \times</math> ULN:
 
 
• Type 1 anti-liver kidney microsomal antibodies, and quantitative total immunoglobulin G (IgG) or gamma
 


AGN-242428

 
Repeat liver chemistry tests (include ALT, AST, ALP, TBL, DBL, IBL, GGT, and LDH) and perform liver chemistry follow-up assessments within 24 to 72 hours.
 
Monitor participants weekly until liver chemistry abnormalities resolve, stabilize, or return to baseline.
 
	
 
globulins.
 
Liver imaging (ultrasound, magnetic resonance, or computerized tomography) and/or liver biopsy to evaluate liver disease; complete the Hy's Law eCRF form and the AESI Form, which is the Adverse Event of Interest Abnormal Liver Function Reporting Form.
 

---	---

AESI = adverse event of special interest; ALT = alanine aminotransferase; AST = aspartate aminotransferase; eCRF = electronic case report form; TBL = total bilirubin; ULN = upper limit of normal

a = New or worsening symptoms believed to be related to liver injury (such as fatigue, nausea, vomiting, right upper quadrant pain or tenderness, or jaundice) or hypersensitivity (such as fever, rash or eosinophilia).

b = All events of AST and/or ALT  $\geq 3 \times$  ULN **and** TBL  $\geq 2 \times$  ULN and alkaline phosphatase  $< 2 \times$  ULN indicate severe liver injury (**potential 'Hy's Law'**) and **must be reported as both an AESI and an SAE** by completing the AESI Form, which is the Adverse Event of Interest Abnormal Liver Function Reporting Form, and sending it to [contact] (or faxing it to the SAE fax number) within 24 hours of learning of the potential Hy's Law case.

c = Includes: Hepatitis A immunoglobulin M (IgM) antibody; hepatitis B surface antigen and hepatitis B Core Antibody (HBcAb); hepatitis C RNA; cytomegalovirus IgM antibody; Epstein-Barr viral capsid antigen IgM antibody (or if unavailable, heterophile antibody or monospot testing); hepatitis E IgM antibody; anti-nuclear antibody; and anti-smooth muscle antibody.

d = PK sample may not be required for participants known to be receiving placebo or non-comparator treatments. Record the date/time of the PK blood sample draw and the date/time of the last dose of study treatment prior to the blood sample draw on the eCRF. If the date or time of the last dose is unclear, provide the participant's best approximation. If the date/time of the last dose cannot be approximated OR a PK sample cannot be collected in the time period indicated above, do not obtain a PK sample. Instructions for sample handling and shipping are in the Laboratory Manual.

AGN-242428

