### 8.1. Discontinuation of Study Treatment

Participants may stop study medication on the basis of intolerance, as determined by AE, vital sign or physical examination findings, clinically important laboratory or ECG findings, or investigator opinion. If a participant does not tolerate study medication, the participant will be observed until the intolerable AE has either resolved or satisfactorily stabilized in the judgment of the investigator, and the participant will be withdrawn from the study.

AGN-242428

A participant will be permanently withdrawn from study medication if any of the criteria in **Table 8-1** are met and considered related to AGN-242428. Re-challenge with AGN-242428 will not be permitted.

**Table 8-1** Safety Criteria for Individual Participants Stopping Study Treatment

Parameter	Definition
Study treatment-related serious adverse event (SAE)	Study treatment-related SAE, as assessed by investigator
Increased liver transaminases a	Aspartate aminotransferase (AST) and/or alanine aminotransferase (ALT) increased to $\geq 5 \times$ upper limit of normal (ULN) c
Increased liver transaminases with increased total bilirubin (TBL) or increased INR	AST and/or ALT increased to $\geq 3 \times$ ULN AND TBL increased to $\geq 2 \times$ ULN or INR $> 1.5^c$
Increased liver transaminases with symptoms a,b	AST and/or ALT increased to $\geq 3 \times$ ULN with symptoms c
Decreased total leukocyte count a	Leukopenia to $< 3000/\mu\text{L}$ [ $< 3.0 \times 10^9/\text{L}$ ]
Decreased total neutrophil count a	Neutropenia to $< 1000/\mu\text{L}$ [ $< 1.0 \times 10^9/\text{L}$ ]
Decreased lymphocyte count a	Lymphopenia to $< 500/\mu\text{L}$ [ $< 0.5 \times 10^9/\text{L}$ ]
Decreased platelet count a	Thrombocytopenia to $< 100,000/\mu\text{L}$ [ $< 100 \times 10^9/\text{L}$ ]
Increased serum creatinine a	Serum creatinine increased to $\geq 2 \times$ ULN
Unspecified	Based on medical judgment of sponsor's Medical Safety Physician, Medical Expert and investigator

a To be confirmed by a repeat of the test within 2 to 5 calendar days.

b New or worsening symptoms believed to be related to liver injury (such as fatigue, nausea, vomiting, right upper quadrant pain or tenderness or jaundice) or hypersensitivity (such as fever, rash or eosinophilia  $> 5\%$ )

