	Study Stop Rules	A participant will be permanently withdrawn from study treatment if any of the criteria below are met and considered related to AGN-242428:

AGN-242428

Parameter Group	Parameter	Value
		
Study Treatment-related SAE
 
Decreased total leukocyte count; Leukopenia < 3000/<math>\mu</math>L (< 3.0 x 10^9/L)
 
Decreased total neutrophil count; Neutropenia < 1000/<math>\mu</math>L (< 1.0 x 10^9/L)
 
Decreased total lymphocyte count; Lymphopenia < 500/<math>\mu</math>L (< 0.5 x 10^9/L)
 
Decreased platelet count; Thrombocytopenia < 100,000/<math>\mu</math>L (< 100 x 10^9/L)
 
Increased serum creatinine; Serum creatinine > 2 x ULN
 
Unspecified safety concern; Upon request by investigator or Medical Safety Physician
 
Increased liver enzymes:
 
 
•ALT and/or AST <math>\geq</math> 5 x ULN
 
•ALT and/or AST <math>\geq</math> 3 x ULN AND TBL <math>\geq</math> 2 x ULN or INR > 1.5
 
•ALT and/or AST <math>\geq</math> 3 x ULN with symptoms
 

AGN-242428

**12.8. Appendix 8: Partial List of Prohibited Medications Which Are Sensitive Substrates for BCRP, OATP1B3, CYP2D6, and CYP2C8 and Strong Inhibitors or Inducers of CYP3A4**

This list of prohibited medications is provided as a guidance. Use of these medications is prohibited unless approved by the investigator or sponsor. This list is not comprehensive and the investigators will consult with the sponsor before allowing concomitant medication use during the trial.

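### Appendix 6 sets liver follow-up pace by bilirubin alone, so in the visible text a stop for INR > 1.5 with bilirubin < 2 × ULN is held only to the slower schedule

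*Protocol*

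**What the plan says.** The Bilirubin or INR row of the stopping criteria in Protocol Appendix 6 reads "AST and/or ALT $\geq 3 \times$ ULN and TBL $\geq 2 \times$ ULN or INR $> 1.5". Table 8-1 (Section 8.1) has the same pair in a row titled "Increased liver transaminases with increased total bilirubin (TBL) or increased INR". That title makes clear that INR is an alternative to bilirubin, each taken together with the raised transaminases. Appendix 7 repeats it among the study stop rules ("ALT and/or AST \geq 3 x ULN AND TBL \geq 2 x ULN or INR > 1.5"), and Section 9.2.8 uses it to define an adverse event of special interest (AESI).

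The required-actions table in Appendix 6 then sets the pace of follow-up under two headings:

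- Faster branch, "If AST and/or ALT \geq 3 \times ULN AND bilirubin \geq 2 \times ULN": repeat the liver tests and "perform liver event follow-up assessments within 24 hours", then "Monitor participant twice weekly until liver chemistry test abnormalities resolve, stabilize, or return to baseline". A specialist or hepatology consultation is recommended.
- Slower branch, "If AST and/or ALT \geq 3 \times ULN AND bilirubin < 2 \times ULN": repeat the liver tests and "perform liver chemistry follow-up assessments within 24 to 72 hours", then monitor weekly. There is no consultation line.

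INR is in neither heading. It appears only in the list of assessments common to all liver stops, as a test to repeat alongside each liver chemistry panel until transaminases start to fall.

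**The concern.** Two markers are treated as alternatives when deciding to stop, but only one of them leads to the faster recheck and the recommended consultation. A participant with AST or ALT ≥ 3 × ULN, INR > 1.5 and bilirubin < 2 × ULN meets the stopping row through INR and then fits only the slower heading.

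What is at stake is participant safety after the stop, in a trial where the liver is a known concern. Section 5.5 reports ALT/AST elevations at one dose level of the 4-week proof-of-concept study. Section 5.4 relies on well-defined follow-up of hepatic enzyme elevations. The case can be detected: Table 9-4 includes INR and liver function tests, and both are kept at the reduced Week 6 and Week 10 draws. The concern does not extend to the analysis. SAP Section 11.1.1 summarises AESIs by treatment group, and follow-up pace is not part of their definition.

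**Working it through.** The plan gives no figure to reproduce. The check compares the stopping rule with the follow-up headings and then does simple visit arithmetic.

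**Step 1. Sort every case with AST or ALT ≥ 3 × ULN.**

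| Bilirubin | INR | Meets the Bilirubin or INR stopping row? | Follow-up heading |
|---|---|---|---|
| ≥ 2 × ULN | any | yes | faster |
| < 2 × ULN | > 1.5 | yes, through INR | slower |
| < 2 × ULN | ≤ 1.5 | no (another row may apply) | slower |

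The second line is the point at issue. No visible text moves it to the faster heading.

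**Step 2. Is the faster branch reserved for a different kind of case?** It is not limited to potential Hy's Law cases, because its heading has no alkaline phosphatase condition and the potential Hy's Law criterion does. Table 8-1 also treats the two markers alike at the stop. The rows for AST/ALT ≥ 5 × ULN and for ≥ 3 × ULN with symptoms carry a footnote asking for confirmation by repeat in 2 to 5 days. The combined bilirubin-or-INR row does not carry that footnote for either marker.

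**Step 3. Are the pace instructions attached to the right headings?** In the text version read here, the table's two columns run together. The placement of the antibody, imaging or biopsy, and Hy's Law form items is therefore uncertain. The pace instructions are not in doubt: the faster heading already has its own 24-hour and twice-weekly lines, so the 24-to-72-hour and weekly lines can belong only to the slower one.

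**Step 4. First repeat.** The faster limit is 24 hours and the slower range is 24 to 72 hours. Against the 24-hour limit, the allowed delay runs from 24 − 24 = 0 to 72 − 24 = 48 hours.

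**Step 5. Number of checks.** Assume that abnormalities persist and that checks are evenly spaced: every 7/2 = 3.5 days (faster) or every 7 days (slower).

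| Counting rule | 14 days, faster v slower | 28 days, faster v slower |
|---|---|---|
| First repeat opens the schedule | 14/3.5 = 4 v 14/7 = 2 | 28/3.5 = 8 v 28/7 = 4 |
| First repeat is additional | 1 + 4 = 5 v 1 + 2 = 3 | 1 + 8 = 9 v 1 + 4 = 5 |

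The slower branch has 2 fewer checks at 14 days and 4 fewer at 28 days under either rule. The 14- and 28-day horizons are chosen for illustration. The protocol ends monitoring when values settle, so a quick recovery gives a smaller difference.

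**The case against.** The strongest reply is that the participant is well protected anyway, and much of this stands.

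- Under Appendix 6, treatment stops at once, the sponsor is told within 24 hours, and INR is rechecked with each liver panel.
- Section 9.2.3 does more than permit extra work. It obliges the investigator to arrange further tests or consultation when medically indicated or when the sponsor asks, and an INR stop of this kind is an AESI.
- Section 9.2.8 requires a search for the cause together with the Medical Safety Physician.
- Section 9.4.4 requires clinically significant laboratory values to be repeated until they settle.

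None of these sets a 24-hour or twice-weekly pace. The INR recheck follows whichever liver-test schedule applies.

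Second, the appendix is largely guidance. Its title and the references in Sections 8.1 and 9.2.8 call the actions suggested, and Section 9.4.4 calls them guidance, although the table header calls them required. The slower times are not a ceiling, and a repeat at 24 hours satisfies both headings.

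Third, no rule says that markers sharing a stopping row must share a follow-up pace. AST/ALT ≥ 5 × ULN with bilirubin < 2 × ULN also takes the slower branch, and that is not questioned here. Aligning INR with bilirubin is a design judgement.

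Fourth, part of the text cannot be seen. Section 2 of the protocol, to which the Synopsis and Section 8.1 refer for testing criteria and further evaluations, is redacted. So is text next to the unscheduled-visit rules in Protocol Section 5.1 and SAP Section 4.0. A faster rule may stand there.

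A reader might go further and infer that such a participant stays on drug, goes unmonitored, or is denied a consultation. The provisions above contradict each of these. A reader might also infer from the amendment history that INR was added to the stopping rules and the headings were overlooked. The documents do not say so, and the point does not need it.

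**Conclusion.** The point holds as a minor one. In the visible text, a stop for INR > 1.5 with bilirubin < 2 × ULN is held only to the slower follow-up, although Appendix 6 treats INR and bilirubin as alternatives for the stop itself.

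The firm size is a 72- rather than 24-hour outer limit for the first repeat, weekly rather than twice-weekly checks, and the loss of one recommendation to consult. The figure of about 4 fewer checks over 4 weeks depends on persistent abnormalities and even spacing. The documents do not say how many participants would be affected. The conclusion also assumes that the redacted text contains no faster rule. No endpoint, stopping rule, reporting duty or planned analysis is affected.

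**What to change.** Reword the two headings in Appendix 6:

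- Faster branch: AST and/or ALT ≥ 3 × ULN AND (bilirubin ≥ 2 × ULN or INR > 1.5).
- Slower branch: AST and/or ALT ≥ 3 × ULN AND bilirubin < 2 × ULN and INR ≤ 1.5.

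The headings then remain mutually exclusive and still cover every case with AST or ALT ≥ 3 × ULN. If Section 2 already contains a faster rule for raised INR, a cross-reference to it would do instead.

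The cost is a wording change plus extra visits and blood draws for any participant stopped in this way: about 4 more over 4 weeks under the same assumptions, and fewer if values settle sooner. The SAP needs no change.
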